Time 0 (T0) Baseline intervention assessments (Visit III): Within one month before week 1 of the intervention phase, all participants (THR, BA, Waitlist, Hybrid) will be individually scheduled to complete the SALT¹²⁷ with the speech therapist at their study site (Colorado or Maine). The speech assessment will be audiotaped and transcribed to allow scoring of this measure. Video and audio files will be stored on a secure, password protected drive on the Colorado and Maine Health sites secure network servers. On the first day of the 10-week intervention (THR, BA, or Hybrid) or wait period, caregivers will complete the ABC-C,⁹⁸ SRS™-2,¹²⁶ EDI,¹²⁸ the WHOQOL-BREF⁹⁵ , and the Crisis Mental Health Care Usage Survey

If caregivers decide to postpone their child's 10-week intervention after they have already completed baseline intervention assessments (Visit III) and their child has completed only up to two intervention lessons, caregivers will be asked to complete an additional baseline assessment (caregiver forms only). The initial completed baseline assessments will not be used for data analyses. Additionally, when the participant is ready to complete their 10-week intervention, they will not attend the one or two lessons they may have previously attended so that they will only complete up to 10 intervention lessons as part of their participation in the study.

Riding center site 10-week intervention (Visits IV-XIII): (See Appendix for an overview of THR and BA interventions).

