Participants (THR, BA, Hybrid in Colorado only) will attend intervention sessions at the riding center in their recruitment state (Colorado or Maine). THR and BA control group times will be between 1:00-5:00 PM in order to collect salivary cortisol when levels typically decline.¹¹¹ Hybrid group times will also occur within this same afternoon time period for consistency, even though salivary cortisol samples will not be collected. Intervention groups (THR, BA, Hybrid) will consist of 2-4 participants, be led by a THR instructor, follow a consistent routine, and learn horsemanship skills via activities tailored to ASD learning styles outlined in the THR manual.¹¹⁶ Each week of the intervention phase (THR, BA or Hybrid), caregivers will complete the ABC-C,⁹⁸ rating their child's behaviors over the past week prior to the current lesson. THR Intervention: Each participant will have an assigned horse and volunteer(s) (one horse leader and up to two side walkers). Similar to the RCT¹¹³, every effort will be made to enable each participant to ride a consistent horse throughout the study. Barn Activity Intervention: Each participant will have one assigned volunteer and will have no contact with horses at the riding center, just view horses at a distance. There will be a life-sized stuffed horse in the BA group for hands-on learning related to the weekly topic.

For THR and BA participants only: To increase compliance with mediator assessments, each week prior to starting the groups, participants will follow a consistent routine of wearing both their Shimmer3 EDA and ECG devices. The Shimmer EDA device will be worn on the wrist of participant's non-dominant hand and the Shimmer3 ECG cardiac monitor will be adhered to the chest wall area using adhesive electrodes. Participants will sit at a group art table with their respective small group (THR or BA) while study personnel will instruct participants to place the 10cm long foam swab rod under their tongue for one minute while watching a 1-minute timer. THR participants will then don their riding helmets and enter the riding arena and the BA will begin their group activity at the group table. Each week after conclusion of the THR and BA interventions, participants will sit with their respective groups (THR or BA) at an art table for 5 minutes followed by another saliva sample.

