Time 1 (T1) Mediator assessments taken weekly during the 10-week intervention, but will only be analyzed for weeks 1, midpoint, and 10. Physiological data (HR, HRV, and EDA) measurements will be taken continuously during the entire intervention lessons. Sections of analysis will be segmented from: (a) Three to five-minute seated art activity baseline before either intervention; (b) 45-minute THR riding or BA activity; (c) 15-minute THR grooming and tacking or BA scrapbook activity; and (d) 5-minutes post intervention that includes a seated art activity. RAs will annotate time and relevant activity levels for each period to correspond to device timestamps. Salivary cortisol samples will be taken during the five-minute seated baseline before THR or BA intervention and again 5 minutes post intervention. Caregivers will complete the Physiological Sample Collection Log each week of the 10-week intervention.

Time 2 (T2) Post- intervention assessments (Visit XIV): On the last day of the 10-week intervention (THR, BA, Hybrid) or waitlist period, caregivers will complete the ABC-C,⁹⁸ SRS™-2,¹²⁶ EDI,¹²⁸ , the WHOQOL-BREF⁹⁵ , and the Crisis Mental Health Care Usage Survey. Within one month of the conclusion of week 10 of the intervention phase, all participants (THR, BA, waitlist, and Hybrid) will be individually scheduled to complete the SALT¹²⁷ with the same speech therapist they saw for the Pre-intervention SALT at the Colorado or Maine hospital site. If there is a speech therapist personnel change from a participant's pre- to post- intervention SALT assessment visit, this change will be noted in the REDCap database to control for personal novelty bias in the analysis.

Time 3 (T3) Six-month post-intervention assessment (Visit XV): Only THR and BA participants will be individually scheduled to complete SALT¹²⁷ with the speech therapist at their study site (Colorado or Maine). During this visit, caregivers will complete the ABC-C,⁹⁸ SRS™-2,¹²⁶ EDI,¹²⁸ , the WHOQOL-BREF⁹⁵ , and the Crisis Mental Health Care Usage Survey. If there is a speech therapist personnel change from a participant's post- to 6-month post- intervention SALT assessment visit, this change will be noted in the REDCap database to control for personnel novelty bias in the analysis.

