Participants will be asked to participate in this study for up to 11 months, depending on their group randomization. During this time and depending on their group randomization status, participants will attend up to 21 study visits described as follows:

- Two initial consent/screen visits (diagnostic and cognitive assessments, intervention riding center site screening)
- One pre-intervention evaluation at the Colorado or Maine subcontract site (within one month) prior to the 10-week intervention (THR/BA or Hybrid) or waiting period. *Note, if caregivers decide to postpone their child's 10-week intervention after they have already completed baseline intervention assessments (Visit III) and their child has completed only up to two intervention lessons, caregivers will be asked to again complete the baseline assessment (caregiver forms only). The initial completed baseline assessments will not be used for data analyses.*
- Ten intervention visits at the riding center (THR, BA or Hybrid group lessons)
- One post-intervention evaluation at the Colorado or Maine subcontract site (within one-month post intervention for THR, BA, Waitlist and Hybrid group participants). Note: The post-waiting period evaluation of the Waitlist group may also serve as the pre-intervention evaluation for their involvement in the Hybrid group unless there is a two-month lag period before the start of their Hybrid group. In such case, the Hybrid group will complete an additional pre-intervention evaluation within one month of the 10-week Hybrid intervention.
- One post-intervention evaluation at the Colorado or Maine subcontract site six-months post intervention for THR or BA group participants only

Recruitment and Retention Plan:

For this proposed study, we will localize recruitment efforts in communities (e.g., hospital psychiatric treatment centers, schools, respite care, local parent autism societies, and mental health care agencies) in the surrounding areas closest to the riding centers in northern and southern Maine regions. Please see Facilities and Resources document for a table to referral sources in those communities.

Retention plan for study assessment periods:

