hybrid intervention (H3b), data during the hybrid treatment period will be compared to within-person outcome data during the wait period. Moreover, we will compare hybrid treatment participants to all BA and THR participants. For both hypotheses 3a and b, LMM models similar to the one for Aim 1 efficacy analysis will be used. Again, the between-group difference in outcome change between baseline and 10 weeks will be used to assess efficacy and tested for statistical significance. The 95% confidence interval for efficacy and corresponding effect size (Cohen's D) will be reported. Any imbalanced confounding variables will be adjusted in the model. To explore whether THR effects are any different between participants recently discharged from the psychiatric hospital and those without recent psychiatric hospitalization, we will compare THR effects between these two groups of THR/BA participants by introducing three extra terms in the model for Aim 1. They include an indicator variable (RecentHosp) for this sub-classification (with or without recent hospitalization) and the intervention*RecentHosp and intervention*RecentHosp*time interaction terms. Contrasts will be set up to test the effect of interest and 95% CI for this effect assessment will be calculated

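### Reusing the post-wait evaluation as the Hybrid baseline conflicts with the baseline timing rule and can put up to two months of untreated time into the Hybrid change (exploratory H3b only)

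*Protocol*

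**What the plan says.** Waitlist children in Colorado go on to the Hybrid program after their 10-week wait. The protocol times their assessments in several places.

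- **Time 0 (T0) Baseline intervention assessments (Visit III), caregiver forms:** "On the first day of the 10-week intervention (THR, BA, or Hybrid) or wait period, caregivers will complete the ABC-C", together with the SRS-2, EDI, WHOQOL-BREF and crisis survey.
- **Same section, SALT:** "Within one month before week 1 of the intervention phase, all participants (THR, BA, Waitlist, Hybrid) will be individually scheduled" for it.
- **Time 2 (T2) Post-intervention assessments (Visit XIV):** "On the last day of the 10-week intervention (THR, BA, Hybrid) or waitlist period, caregivers will complete the ABC-C" and the other forms. SALT follows within a month after week 10.
- **Duration of Participation, reuse rule:** "The post-waiting period evaluation of the Waitlist group may also serve as the pre-intervention evaluation for their involvement in the Hybrid group". The one exception to this reuse is worded "unless there is a two-month lag period before the start of their Hybrid group". If that lag occurs, "the Hybrid group will complete an additional pre-intervention evaluation within one month of the 10-week Hybrid intervention".
- **Riding center site 10-week intervention (Visits IV-XIII):** "Each week of the intervention phase (THR, BA or Hybrid), caregivers will complete the ABC-C", rating the week before the current lesson.
- **Data Analysis Plan, Exploratory AIM 3 (H3b):** "data during the hybrid treatment period will be compared to within-person outcome data during the wait period". Hybrid children are also compared with all BA and THR participants. The measure is change from baseline to 10 weeks.

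No section says which value is the Hybrid baseline for each outcome.

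**The concern.** The two timing rules cannot both hold for every Hybrid child. A post-wait evaluation that is, say, seven weeks old when Hybrid starts is acceptable under Duration of Participation. It is not a day-1 set of forms, and its SALT may lie outside the one-month window.

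Two consequences follow when reuse occurs. First, the Hybrid change begins at the end of the wait and so includes the untreated gap before lesson 1. The THR, BA and wait-period changes on the caregiver forms contain no such gap. Second, in the within-child comparison a single rating is both the end of the wait change and the start of the Hybrid change, so its error enters the contrast twice.

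The protocol rejects old baselines elsewhere. If a family postpones after Visit III, the caregiver forms are repeated and the first set is not analyzed. The reuse rule departs from that principle for Hybrid alone. At stake is H3b, which carries the trial's dose question in 20 to 24 children.

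**Working it through.** **1. The plan's own figure.** The only Aim 3 figure under Power analysis is a detectable Cohen's d of 0.9 (20 vs 20) or 0.74 (20 vs 56) at 80% power. With a two-sample t-test, two-sided 5% (two-sided is assumed) and noncentrality d / √(1/n₁ + 1/n₂), solving for 80% power gives 0.909 and 0.739. The figures reproduce and are not in dispute. They are for independent groups and do not describe the within-child contrast.

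**2. Time span, caregiver forms.**
- Longest lag before a new evaluation is required: just under 2 months = 2 × 365.25 / 12 / 7 = 8.7 weeks.
- Hybrid change with reused forms: up to 10 + 8.7 = 18.7 weeks.
- Untreated share at that extreme: 8.7 / 18.7 = 47%.
- THR, BA and wait changes: 10 weeks.

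**3. Time span, SALT.** All arms may have a pre-intervention SALT up to one month old, about 4.3 weeks. A reused post-wait SALT can be up to about 8.7 weeks old if it was done at the end of the wait. The excess over the permitted window is therefore up to about one month.

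**4. Shared rating.** Let W0 and W10 be the wait ratings, H0 and H10 the Hybrid ratings, and s² the within-person error variance, with errors independent.
- Separate Hybrid baseline: (H10 − H0) − (W10 − W0) has variance 1 + 1 + 1 + 1 = 4 s².
- Shared baseline (H0 = W10): H10 − 2·W10 + W0 has variance 1 + 4 + 1 = 6 s².
- Standard error ratio: √(6/4) = 1.22.
- Correlation of the two changes: −s² / 2s² = −0.5.

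As a variant, assume true scores with an autocorrelation of 0.98 per week and reliability from 0.6 to 0.9, at lags of 0 to 8.7 weeks. The standard error ratio is then 1.09 to 1.22 and the correlation −0.24 to −0.41.

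Under the independent-error case, the difference detectable with 80% power in a paired test, in units of the SD of one period's change, is:

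| n | Separate baseline | Shared baseline |
|---|---|---|
| 20 | 0.93 | 1.14 |
| 24 | 0.85 | 1.03 |

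**5. Bias from sharing.** The expected error of H10 − 2·W10 + W0 is zero when each rating error has mean zero. Sharing costs precision; it does not shift the mean contrast. Only the untreated gap can shift it.

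**6. Which outcomes are exposed.** ABC-C is completed at every Hybrid lesson for the preceding week, so a fresh pre-treatment rating exists at lesson 1 however the reuse rule is read. SRS-2, EDI, WHOQOL-BREF, the crisis survey and SALT have no weekly counterpart.

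**The case against.** **The reuse rule may concern SALT only.** It speaks of an *evaluation* at the clinical site, and the visit scheduled within one month is the SALT visit. The caregiver forms are tied separately to the first and last day. On that reading the day-1 rule stays in force and only a one-month versus two-month mismatch for SALT remains. This reading is possible, but Visits III and XIV both list the caregiver forms, so the wider reading is fair too. The SALT conflict survives either way.

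**A shared middle assessment is ordinary in a wait-then-treat design.** This is true. The planned mixed model, like the Aim 1 model with its unstructured covariance, can represent the correlation. It does not supply the missing second rating. A reader might infer that a chance high rating at the end of the wait systematically favors Hybrid. It does so in one child's data, but independent errors average out over children.

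**A points figure is tempting but unsupported.** A reader might apply the BA change under Power analysis (2.3 points in 10 weeks) to the gap: 0.87 × 2.3 = 2.0 points, or 43% of the 6.9 − 2.3 = 4.6-point THR-BA difference. That calculation uses ABC-C irritability, for which a lesson-1 rating is collected. It treats the change under an active program as untreated drift, although whether BA differs from waiting is what H3a asks. It also presumes improvement, when children could worsen.

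**The extreme may be rare.** Reuse is optional and the protocol gives no expected lag, so 18.7 weeks is a ceiling. This stands.

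**Aim 3 is exploratory.** This also stands. Nothing here touches Aims 1 and 2, the primary outcome analysis or the stated power.

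**Conclusion.** The two sections conflict and should be reconciled. The conflict with the one-month SALT window holds on any reading. The conflict with the day-1 rule holds if the reused evaluation includes the caregiver forms.

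Where reuse occurs, the Hybrid change for the non-ABC-C outcomes can include up to about two months without treatment: up to about 18.7 weeks instead of 10 for the forms, and a pre-intervention gap of up to two months instead of one for SALT. The resulting distortion in the comparison with THR and BA cannot be sized or signed from the document. ABC-C is affected only if its lesson-1 rating is passed over.

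The shared rating makes the within-child contrast less precise, by a factor of about 1.09 to 1.22 in standard error. That range rests on assumed error structures, and the mean is not biased. The consequences are confined to exploratory H3b. The point still deserves correction, because a later analysis plan cannot recover baselines that were never collected.

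**What to change.** Amend Duration of Participation to agree with the Time 0 section, and name the Hybrid baseline for each outcome:

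- **SRS-2, EDI, WHOQOL-BREF and crisis survey:** the forms completed on day 1 of Hybrid.
- **ABC-C:** the rating at Hybrid lesson 1, which is already collected.
- **Post-wait forms:** used only as the end of the wait period.
- **SALT:** the post-wait sample may be reused only if it falls within one month before Hybrid week 1; otherwise repeat it.

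The cost is one questionnaire set for about 20 to 24 families at a visit they already attend, and an occasional repeat SALT when the gap exceeds one month. ABC-C needs no extra collection.

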*Aberrant Behavior Checklist-Community (ABC-C)*⁹⁸, a 58-item behavior symptom checklist commonly used as a primary outcome measure in intervention studies with the ASD population, ⁹⁸ is described previously.^{13,15} The ABC-C will be completed weekly during the 10-week intervention by a designated consistent caregiver for each participant. The ABC-C Irritability scale will be used as a study screener (see inclusion criteria and screening methods sections.

*Social Responsiveness Scale™, Second Edition (SRS™-2)*¹²⁶ is a 65-item caregiver-report measure that evaluates social impairments in ASD. The SRS™-2 generates five treatment subscales (social awareness, social cognition, social communication, social motivation, autistic mannerisms), also described previously.^{13,15}

*Systematic Analysis of Language Transcripts (SALT)*¹²⁷ provides standardized guidelines to elicit, transcribe, and analyze language samples from individuals, including those with ASD. The SALT also provides language analysis programs to compute a vocabulary diversity quotient from transcripts entered into the database. A five-minute expressive language sample will be elicited by each participant and recorded by the project's Speech Therapist, blind to participants' randomized group assignment, also described previously.^{13,15} The speech therapists from Colorado and Maine sites will follow a standard administration protocol of prompts to obtain the 5-minute speech sample from participants at the pre- and post-intervention and 6-month time periods. The Colorado and Maine site speech therapists will develop administration and scoring reliability on the SALT¹²⁷ by the Colorado SALT trainer speech therapist reviewing a videotaped administration of the Maine site speech therapists SALT administration and then giving them feedback. The Maine and Colorado site speech therapists will also achieve an (at least) 80% scoring reliability on three consecutive SALT¹²⁷ transcriptions assessments.

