Inclusion criteria: (1) Aberrant Behavior Checklist-Community (ABC-C) ^{31,98} Irritability subscale score ≥ 8 ; (2) Leiter-II¹⁰⁶ Nonverbal IQ standard score ≥ 40 ; (3), meeting the Symptom Criterion score (minimum number of symptoms necessary for a DSM-V²⁷ mood, anxiety, or ADHD diagnosis) on the Child & Adolescent Symptom Inventory 5 (CASI-5);¹⁰⁷ and (4) a confirmed diagnosis of ASD by meeting clinical cut-offs on the Social Communication Questionnaire (SCQ)¹⁰⁸ (≥ 11)¹⁰⁹ and Autism Diagnostic Observation Schedule-2 (ADOS-2).¹¹⁰ Only one child with ASD per family will be included in the study to maintain independent observation of participants. Participants will also require a consistent caregiver (i.e., parent or legal guardian) to complete study outcome measures. We will not exclude participants taking medications, as this is a common occurrence for the target population. However, information regarding medications, dosages, and any changes during the study will be collected from caregivers. Medications or substances that could affect cardiovascular or electrodermal activity (e.g., amphetamines, anxiolytics, anticholinergics, beta blockers) or cortisol levels.¹¹¹ (i.e., smoking or regularly use oral, inhaled, or topical steroids), will be flagged and participant's physiological data collected may be excluded or controlled for in the analyses.

Exclusion criteria: Potential participants will be excluded for any of the following reasons: (1) medical or behavioral issues (e.g., animal abuse or phobia to horses) that prevent participation; (2) being a ward of the state; (3) is judged during the riding center screening to have significant riding experience, as the THR manualized curriculum¹⁶ is designed for beginner riders; (4) exceeding weight limits determined by the individual riding center sites' (Colorado and Maine) safety policies (5) vision, hearing, or physical impairments that would prevent participants from being able to be accurately evaluated (e.g. needing to see materials, see others, respond to questions) by study diagnostic measures or (6) unable to engage safely and independently with horses and others at the riding center. Of note, participants will not be allowed to begin baseline assessments until at least six months have passed from the time they last engaged in mounted EAAT, given pilot evidence for the six-month maintenance of THR effects.¹¹²

Study Design and Research Methods

(See Appendix for Calendar of Events/Timetable Document)

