Treatment Randomization and Termination: Participants at the Colorado site will be randomly assigned to either a THR group, BA control group or waitlist group. Participants at the Maine subcontract site will be randomly assigned to either a THR group or BA control group. BA control participants who are not randomized in the THR group may experience frustration if they are not able to interact with horses as part of their involvement in the study. However, participants in the BA control group will be offered the opportunity to receive a one-hour free horseback riding group lesson at their respective sites' riding center that will occur after they complete 10-week post-intervention SALT assessment. Other than the BA activity 1 free THR lesson, BA and THR participants will need to refrain from riding horses until their 6-month post-assessment is completed. Participants randomized to the 10-week waitlist (CO site only) will then be involved in the Hybrid group that included five weeks of BA followed by five weeks of THR. However, the waitlist participants may experience disappointment that they are not immediately able to interact with horses. The THR, BA, and Hybrid groups may view the termination of the study period as a loss of treatment benefits. If participants wish to continue THR beyond the study period, the therapeutic riding sites (CO or ME) have availability for those who wish to continue these interventions on a fee for service basis.

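### Outside riding by wait-list children during the 10-week wait is neither restricted nor recorded, which leaves the exploratory BA-versus-wait-list comparison (H3a) open to dilution

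*Protocol*

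**What the plan says.** Under Treatment Randomization and Termination, apart from one free lesson for BA children, "BA and THR participants will need to refrain from riding horses until their 6-month post-assessment is completed". The same paragraph then turns to the wait-list and says only that "the waitlist participants may experience disappointment that they are not immediately able to interact with horses". That describes what the study offers them; it gives no instruction about riding elsewhere.

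The eligibility section has a general washout: "participants will not be allowed to begin baseline assessments until at least six months have passed from the time they last engaged in mounted EAAT". It names no arm, but it is tied to the start of baseline assessments and to mounted equine-assisted activity.

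Under Duration of Participation, "The post-waiting period evaluation of the Waitlist group may also serve as the pre-intervention evaluation for their involvement in the Hybrid group", unless a two-month lag intervenes, in which case a new evaluation is done before Hybrid.

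The analysis text for Aim 3 compares wait-list with BA (H3a) on change from baseline to 10 weeks. For H3b it compares each child's Hybrid period with that child's own wait period. The rationale for Aim 3 explains why the arm exists: BA children improved in the earlier trial, and without an untreated comparator that improvement could not be interpreted.

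**The concern.** A no-intervention arm does its job only if the children in it do not obtain the active ingredient elsewhere. Here the two arms that receive a programme are told not to ride, and the arm that receives nothing is not. By the Protocol's own account, riding effects appeared by week five in the earlier trial and may last six months, so riding taken up early in a 10-week wait could reach the week-10 outcome. The Protocol also expects wait-list families to be disappointed at having to wait for the horses.

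If some wait-list children ride and benefit, the wait-list arm improves and BA looks less effective than it is. A null H3a result could then mean either that BA does nothing or that the control was contaminated. Without a record of outside riding, the analyst could not tell these apart afterwards. The same riding could also affect H3b, because the wait period is its within-child comparator and the post-wait evaluation may be its starting point.

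**Working it through.** **Which rule covers what**

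| Rule | Arms | Period | Activity |
|---|---|---|---|
| No riding (Treatment Randomization and Termination) | THR and BA | until the 6-month assessment | any horse riding |
| Washout (eligibility) | all | six months before baseline | mounted equine-assisted activity |
| Rule for the 10-week wait and the gap before Hybrid | none found | – | – |

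The caregiver log of sleep, stressors and medication belongs to the THR and BA weeks, so it does not record riding during the wait.

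**Timing.** A ride at any point in the wait falls at most 10 weeks before the post-wait evaluation. Six months is about 26 weeks. Any mounted equine-assisted activity during the wait therefore lies inside the window that the Protocol itself treats as too recent for a baseline.

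**The plan's own figure.** The Power analysis gives minimum detectable effects of 0.9 (20 versus 20) and 0.74 (20 versus 56) at 80% power. With two-sided alpha of 0.05 (sidedness is not stated, so this is an assumption), d = (1.960 + 0.842) × √(1/n1 + 1/n2):

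- 20 versus 20: 2.802 × 0.3162 = 0.886; the t-test solution is 0.909.
- 20 versus 56: 2.802 × 0.2605 = 0.730; the t-test solution is 0.739.

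Both stated values reproduce. The comparison can detect only large effects, so it has little room for dilution.

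**Weight of one child.** 1/20 = 5% of the arm. The Randomization section plans at least 24 completers, which gives 1/24 = 4.2%.

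**Illustration of dilution.** The documents give neither a rate of outside riding nor a BA-versus-wait-list effect. Suppose:

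- the true effect d equals the minimum detectable effect;
- a fraction f of wait-list children ride;
- each rider gains the full THR benefit, 0.62 above BA (the figure stated in the Power analysis);
- the standard deviation is unchanged.

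Then observed d = d − f × (d + 0.62). For f = 10% and d = 0.90: 0.90 − 0.10 × 1.52 = 0.75.

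| f (children of 20) | 20 vs 20: observed d | power | 20 vs 56: observed d | power |
|---|---|---|---|---|
| 0% (0) | 0.90 | 79% | 0.74 | 80% |
| 10% (2) | 0.75 | 64% | 0.60 | 63% |
| 20% (4) | 0.60 | 45% | 0.47 | 43% |
| 30% (6) | 0.44 | 28% | 0.33 | 24% |

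Full THR benefit for every rider is an upper-end assumption. The table shows sensitivity and does not forecast what will happen.

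**The case against.** **The silence may be innocent.** The no-riding sentence ends at the 6-month assessment, which only THR and BA children have. It probably serves Aim 2, so naming those two arms is natural. That explains the wording, but it leaves the wait without a rule. A reader might infer that the Protocol permits wait-list riding. It does not say so; it is silent. Consent pages and the appendix calendar are not shown and may carry an instruction.

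**The washout may already act.** If the post-wait evaluation counts as a baseline assessment for Hybrid, a child who did mounted equine-assisted activity during the wait could be barred from starting Hybrid on time. That may deter families, and it means one cannot say the Hybrid baseline would be spoiled. The objection stands in part: the washout would not remove such a child from H3a, and it does not reach ordinary recreational riding.

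**Rating frequency.** A reader might go further and argue that the arms are also measured differently, because "Each week of the intervention phase (THR, BA or Hybrid), caregivers will complete the ABC-C", with the wait period not named. The documents do not support treating this as a flaw in H3a. The contrast uses change from baseline to 10 weeks, and wait-list caregivers rate at both points: "On the first day of the 10-week intervention (THR, BA, or Hybrid) or wait period, caregivers will complete the ABC-C", and "On the last day of the 10-week intervention (THR, BA, Hybrid) or waitlist period, caregivers will complete the ABC-C". No size or direction for an effect of repeated rating can be drawn from the documents. Weekly monitoring would also make the arm less of a no-intervention control. At most, the difference in frequency deserves a line among the limitations.

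**Aim 3 is exploratory.** This is correct, and it limits the weight of the point.

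**Conclusion.** The gap is real but minor. In the text shown, riding outside the study during the wait, and up to Hybrid, is neither restricted nor recorded for wait-list children, whereas BA and THR children are told not to ride. If such riding occurs and helps, it biases H3a towards no difference and could affect the evaluation that may serve as the Hybrid baseline. How far is unknown: the effect is zero if nobody rides. Under the upper-end assumptions above, two riders in 20 would lower power from 79% to 64% in the 20-versus-20 comparison. The conclusion rests on the absence of a rule in the pages available and on riding being beneficial, which is the Protocol's own premise. No stated sample size or detectable effect changes, and Aims 1 and 2 are unaffected.

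**What to change.** 1. Under Treatment Randomization and Termination, extend the refrain-from-riding condition to wait-list/Hybrid participants, from T0 until the post-Hybrid assessment. Word it as riding outside study sessions, because Hybrid itself contains five weeks of THR.
2. At the post-wait visit, ask whether the child rode during the wait, and record the answer. Ask again if a new pre-Hybrid evaluation is needed.
3. Keep H3a as randomized for the main result, and report it with and without children who rode as a sensitivity analysis. Excluding riders is a selection made after randomization, so it should not replace the main result.
4. If the wait-list arm is already complete, ask families retrospectively and report the asymmetry as a limitation.

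No weekly ABC-C ratings during the wait are needed.

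The cost is one sentence in the Protocol and consent form, and one question at a visit already scheduled. The restriction on families would last about 10 + 10 = 20 weeks plus any gap before Hybrid. BA and THR families already accept 10 weeks plus six months, about 36 weeks.
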